PROTOCOL

Background

1. Provide the scientific background, rationale and relevance of this project.

Answer/Response:

Transversus Abdominis Plane (TAP) block is a useful tool in pain management after abdominal surgery. It is a regional nerve block that targets T6-L1 thoracolumbar nerves running in the plane between internal oblique and transversus abdominis muscle. It is shown to help with post-operative pain management, reducing pain scores and narcotic pain medication use, as well as promoting earlier return to activity and recovery.^{1,2} TAP block became a very popular, safe, and effective therapeutic adjunct for many different abdominal surgeries ranging from obstetric procedures to general surgery procedures like colorectal surgery.^{3,4} Furthermore, it is used in plastic surgery procedures such as Deep Inferior Epigastric Perforator (DIEP) free flap or Transverse Rectus Abdominis Myocutaneous (TRAM) flap, as they involve extensive amount of abdominal soft tissue incision. Previous studies have shown that TAP block in these procedures significantly reduce post-op pain and narcotic pain medication use.^{5,6} More recently, Exparel (liposomal bupivacaine) has risen to spotlight for providing a longer, sustained local anesthesia. Various surgical disciplines have adopted this agent as part of their pain management protocol. However, there are no literatures that describe the effect of TAP block using Exparel for breast free flap population. We hypothesize that delivering TAP block with Exparel (vs. plain bupivacaine) will provide longer regional blocking effect, hence aiding in pain control and recovery postoperatively.

Objectives/Hypothesis

Answer/Response:

- We hypothesize that liposomal bupivacaine (Exparel) TAP block will provide longer pain control compared to plain bupivacaine TAP block in abdomen-based free flap breast.
- Primary outcome = post-op pain scores during hospitalization, post-op narcotic pain medication use during hospitalization, post-op narcotic pain medication use after discharge (within 30 days of discharge)
- Secondary outcome = Length of stay, Post-op nausea and vomiting (PONV)

Study Design: Biomedical

1. Will controls be used?

Answer/Response: Yes

► IF YES, explain the kind of controls to be used.

Answer/Response: Usual care, TAP block with plain bupivacaine

2. What is the study design?

Answer/Response: Randomized, single-blind control study

3. Does the study involve a placebo?

Answer/Response: No

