Human Participants

Ages: 18 and older

Sex: Female

Race: Any

Subjects- see below

1. Provide target # of subjects (at all sites) needed to complete protocol.

Answer/Response:

100 participants

2. Describe expected rate of screen failure/ dropouts/withdrawals from all sites.

Answer/Response:

Minimal.

Once the patient consents to the study, it is unlikely that they will drop out or withdrawal afterwards given that this is part of a usual care pain management protocol. No extra follow up is required for patients and all the outcomes will be part of a usual post-op data that will be recorded in Epic.

3. How many subjects will be enrolled at all sites?

Answer/Response:

This is a single site study – enrollment at UVA only.

4. How many subjects will sign a consent form under this UVA protocol?

Answer/Response:

All participants (100)

Inclusion/Exclusion Criteria

1. List the criteria for inclusion

Answer/Response:

- All female patients who are 18 years or older who will undergo unilateral or bilateral abdomen-based free flap breast reconstruction at UVA Medical Center from February 2021 to January 2024.

2. List the criteria for exclusion

- Answer/Response: Subjects with ages <18 years

- Allergy to local anesthetic
- Inability to tolerate usual postoperative pain management regimen (Tylenol, Toradol, and Oxycodone PRN) for any reason
- Subjects who cannot read or understand English
- Subjects who are pregnant (self-reported)

3. List any restrictions on use of other drugs or treatments.

Answer/Response: None

Statistical Considerations

1. Is stratification/randomization involved?

Answer/Response: Yes

► IF YES, describe the stratification/ randomization scheme.

Answer/Response:

Random number generator will be used to enroll a subject into control TAP vs. Exparel TAP block group after consent is obtained before surgery. Patients will be blinded to their TAP block method. Surgeons/PI/ study coordinators will not be blinded to randomization. Surgeons/ PI/ study coordinators will have access to the randomization scheme.

► IF YES, who will generate the randomization scheme?

	Sponsor
	UVA Statistician.  Answer/Response:
	UVA Investigational Drug Service (IDS)
	Other:  Answer/Response: Study coordinator/ medical staff in plastic surgery clinic

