5. What is your plan for secondary variable analysis?

Answer/Response:

Secondary outcomes will include LOS and PONV.

Two-sample t-tests or Mann-Whitney U tests will be employed for secondary variable analysis.

Exploratory multivariate analysis will be employed to determine potential confounding variables and attempt to determine the focus for future studies to determine independent factors associated with various outcomes.

6. Have you been working with a statistician in designing this protocol?

Answer/Response: Yes

IF YES, what is their name?

Answer/Response: [name]

7. Will data from multiple sites be combined during analysis?

Answer/Response: No

Study Procedures-Biomedical Research

1. What will be done in this protocol?

Answer/Response:

Participants will either receive plain bupivacaine TAP block (control/ usual care) or Exparel TAP block mix (experimental/ mix of Exparel and plain bupivacaine). Post-op data will be recorded in Epic and will be analyzed.

All the subjects will be recruited in UVA plastic surgery clinic when qualifying patients come in for pre-operative visits.

2. If this protocol involves study treatment, explain how a subject will be transitioned from study treatment when they have completed their participation in the study.

Answer/Response: N/A

Subject Compliance with Study Procedures

1. Explain how the study team will monitor the subject for compliance with the study procedures.

(e.g. study team will administer study drug/ study interventions, study drug inventory of dispensed and returned drug, diary etc.)

Answer/Response: N/A

2. Describe criteria for when a subject is considered to be non-compliant with study procedures.

(e.g. subject returns more than 20% of the study drug, subject misses 20% of study visits)

Answer/Response: N/A

Bibliography

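### The plan gives coordinators and the PI knowledge of the arm and masks no one who extracts or analyses outcomes, although nothing in it requires those people to know the arm.

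*Combined protocol and SAP*

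**What the plan says.** The protocol's Study Design section labels the trial "Randomized, single-blind control study". Statistical Considerations, item 1, adds that "Patients will be blinded to their TAP block method", that "Surgeons/PI/ study coordinators will not be blinded to randomization", and that "Surgeons/ PI/ study coordinators will have access to the randomization scheme". The scheme itself is to be produced by "Study coordinator/ medical staff in plastic surgery clinic"; the boxes for a statistician and for the investigational drug service are not ticked.

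On data collection, Human Participants, item 2, says that "all the outcomes will be part of a usual post-op data that will be recorded in Epic", and Study Procedures, item 1, says only that "Post-op data will be recorded in Epic and will be analyzed". Neither names the person who extracts or analyses the data, or says whether that person knows the arm.

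Objectives/Hypothesis lists pain scores, in-hospital opioid use and opioid use within 30 days of discharge as primary, with length of stay and nausea/vomiting as secondary. It expects the Exparel block to control pain for longer. Statistical Considerations, item 3, sizes the trial on narcotic requirement.

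**The concern.** The person who gives the block may have to know the product. The plan goes further. It unblinds the PI and the coordinators without giving a reason, and it is silent about extractors and analysts. Coordinators are a natural choice for pulling outcomes from the chart, so the text as it stands allows the arm to be known at the point where opioid totals and length of stay are derived.

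Where a record is incomplete or ambiguous, someone who knows the arm and expects Exparel to do better can resolve it in that direction without intending to. The opioid total after discharge is the likeliest place: the plan gives no source or method for it and requires no extra follow-up. The analysis is exposed too. Statistical Considerations, item 4, selects covariates by univariate p-values, and item 5 leaves open the choice between a t-test and a Mann-Whitney test for the secondary outcomes. A shift introduced in this way cannot be told apart from a drug effect, and more patients would not remove it.

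**Working it through.** **1. Who knows the arm, and who needs to.**

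| Role | What the plan says | Does a stated procedure need the arm? |
|---|---|---|
| Patient | blinded | no |
| Surgeon | not blinded, has the scheme | possibly, if giving the block |
| PI | not blinded, has the scheme | none stated |
| Study coordinator | not blinded, has the scheme, may generate it | only if acting as list holder |
| Outcome extractor | not described | none stated |
| Analyst | not described | a group label is enough |

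One collected item does need the arm: the type of TAP block, in the data list under Statistical Considerations, item 2. It can be recorded separately from the outcomes.

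**2. The plan's own figure.** Inputs from Statistical Considerations, item 3: 50 per arm, SD 10 mg, alpha 0.05, 80% power, detectable difference 5.66 mg.

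- SE of the difference = 10 × √(2/50) = 2.0 mg.
- 5.66 / 2.0 = 2.83 standard errors. A two-sided t-test on 98 degrees of freedom (critical value 1.984) then has 80.0% power.
- A one-sided test would give 4.97 mg, so the table is two-sided. Its other rows (0.57, 2.83 and 8.49 mg at SD 1, 5 and 15) also reproduce.

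The sample-size arithmetic is sound and is not at issue here.

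**3. Scale of a shift unrelated to the drug.** Assume no true effect and a between-arm shift of b mg. The chance of a significant result is P(|T| > 1.984), where T is noncentral t with 98 degrees of freedom and noncentrality b / SE, and SE = SD × √(2/50) = 0.2 × SD. The values of b are assumptions; the documents give none.

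| SD (mg) | SE (mg) | b = 0 | b = 1 mg | b = 2 mg | b = 3 mg |
|---|---|---|---|---|---|
| 5 | 1.0 | 5% | 17% | 51% | 84% |
| 10 | 2.0 | 5% | 8% | 17% | 32% |
| 15 | 3.0 | 5% | 6% | 10% | 17% |

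For example, at SD 10 and b = 2, noncentrality is 2 / 2.0 = 1.0 and the rejection rate is 16.8%. At SD 10 all three shifts are below the 5.66 mg the trial is sized to detect. The plan also tabulates SD 1; its detectable difference of 0.57 mg is already smaller than the smallest shift assumed here, so that row is not informative for this purpose.

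**The case against.** Single-blind is a declared design, stated openly and without contradiction, so this is not an error in the plan. That stands; the point is a request for improvement. The label does not, however, explain why people with no part in giving the block should know the arm.

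Patients are blinded, they report their own pain, and they may ask for as-needed oxycodone within a usual regimen that the exclusion criteria presuppose for both arms. That stands too: pain scores and much of in-hospital use are partly protected. Exposure is greater for opioid totals after discharge and for length of stay.

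The calculation shows what a shift of a given size would do, whatever its source. It is not evidence that such a shift will occur, and the result depends heavily on the SD, which the plan itself calls uncertain. That is accepted, and the table should be read only as an indication of scale.

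A reader might infer more: that only the patient is masked, that unmasked staff control prescribing, discharge and abstraction, and that opioid totals and length of stay will therefore drift toward Exparel. The documents do not support this. They do not say who does any of these tasks, and they leave the masking of ward nurses, extractors and the analyst undescribed. They also define the opioid outcome as a total in mg, and length of stay needs little judgement to extract.

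**Conclusion.** The concern holds as a moderate and avoidable weakness. The plan gives the arm and the scheme to the PI and coordinators, masks no extractor or analyst, and states no procedure that requires them to know. Masking extraction and coding the arms for analysis would be a cheap and specific safeguard.

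How much bias would arise without it cannot be estimated from the documents. The false-positive rates, 8% to 32% at SD 10 mg and 6% to 84% across SDs of 5 to 15 mg, rest on assumed shifts of 1 to 3 mg and no true effect. It would be wrong to read them as the trial's actual error rate. It would also be wrong to treat masked extraction as a complete remedy: if unmasked surgeons also prescribe or discharge, which the plan does not say, that route stays open.

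**What to change.** In Statistical Considerations, item 1, replace the two sentences on blinding and access so that:

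- Only the list holder and the team preparing and giving the block have access to the list. The PI and other coordinators do not, unless they belong to that team.
- A coordinator or clinic staff member without list access extracts pain scores, opioid totals, length of stay and nausea/vomiting, working from an Epic extract that omits the block entry.
- The list holder records the TAP block item separately and merges it with the outcomes as a coded arm.
- The primary analysis is run on coded arms, and the code is revealed only once that analysis is final.

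The block should be charted for clinical care as it is now; the change concerns only the research extract. The trial report should say that surgeons were unmasked and, if they prescribed or decided discharge, that this remains a source of possible bias.

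The cost is a wording change, a small split of duties and a merge step. The roles are already named in the plan, but it does not give staff numbers, so the sponsor should confirm that the list holder and the extractor can be different people.

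### The unblinded study team generates the randomization scheme and may see it, and the protocol describes no allocation concealment or logged release.

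*Combined protocol and SAP*

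**What the plan says.** Statistical Considerations, question 1, gives the method and timing: "Random number generator will be used to enroll a subject into control TAP vs. Exparel TAP block group after consent is obtained before surgery". On blinding it says "Surgeons/PI/ study coordinators will not be blinded to randomization", and the next sentence is "Surgeons/ PI/ study coordinators will have access to the randomization scheme". Only patients are blinded.

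The form then asks "who will generate the randomization scheme". The sponsor, statistician and Investigational Drug Service (IDS) boxes are unticked. The ticked box is Other, completed as "Study coordinator/ medical staff in plastic surgery clinic".

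Study Procedures, question 1, places all recruitment in that same clinic, at pre-operative visits. Among the exclusions (Inclusion/Exclusion Criteria, question 2) is "Inability to tolerate usual postoperative pain management regimen (Tylenol, Toradol, and Oxycodone PRN) for any reason". Human Participants, question 4, plans 100 consents, and question 2 of that section expects almost no losses: "Once the patient consents to the study, it is unlikely that they will drop out or withdrawal afterwards".

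Nowhere does the protocol mention envelopes, central or pharmacy allocation, an independent holder of the scheme, or a dated record of each assignment. It states no blocks or strata.

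**The concern.** This is not a complaint about blinding. The trial is openly single-blind, and a surgeon may know the arm at operation. Allocation concealment is a separate matter: whoever recruits should not know the next assignment until the patient has been entered. It is achievable in an open-label trial, and with an unblinded team it is the main protection at entry.

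Here one group may generate the scheme, see it, recruit against it and carry it out. If patients expected to need more opioid end up more often in one arm, the comparison of postoperative narcotic requirement is confounded. The planned multivariate adjustment (Statistical Considerations, question 4) can remove bias from a factor that is recorded accurately and passes the p < 0.1 screen. It cannot reliably remove bias from clinical judgement that is recorded poorly or not at all. Concealment that has been lost cannot be restored after enrolment.

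**Working it through.** **Two readings of the text.** The documents do not say whether the scheme is an advance list or a draw per patient. The form item about who generates a scheme leans towards a list; the sentence placing the draw after consent fits a draw per patient.

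- *(a) Advance list.* The access rule lets the team see the next assignment before approaching a patient, judging eligibility or taking consent. Inclusion is broad, but the tolerance exclusion leaves room for judgement.
- *(b) Draw after consent.* There is no earlier assignment to see, so access is not the problem. The weakness is a draw by an unblinded team with no planned log and nothing to stop it being repeated.
- *Both.* There is no rule for patients removed after assignment. Removals would show as a shortfall or as extra consents against the planned 100, but they are not prevented.
- No blocks are stated, so nothing stated makes the next assignment predictable from past ones.

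**The protocol's own figure.** Inputs from Statistical Considerations, question 3: 50 per arm, SD 10 mg, alpha 0.05, power 80%. The normal approximation gives 10 × √(2/50) × (1.960 + 0.842) = 5.60 mg. The exact two-sided t-test gives 5.66 mg, as stated. The sample size is sound and is not affected by this point.

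**Illustration 1: an assumed shift.** Let the true treatment effect be zero and let selection shift the arm difference by b mg. The standard error is 10 × √(2/50) = 2 mg, so the noncentrality parameter is b/2 with 98 degrees of freedom.

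| Assumed b | Share of 5.66 mg | Noncentrality | Two-sided type I error |
|---|---|---|---|
| 0 mg | 0% | 0 | 5.0% |
| 1 mg | 18% | 0.5 | 7.9% |
| 2 mg | 35% | 1.0 | 16.8% |
| 3 mg | 53% | 1.5 | 31.8% |

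**Illustration 2: how such a shift could arise, reading (a) only.** All of the following is assumed:

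- Half of patients carry a factor worth d = 5 or 10 mg of opioid.
- Total SD stays at 10, so the residual SD is √(100 − d²/4) = 9.68 or 8.66.
- Arms stay at 50/50.
- Five times, the order of two patients is exchanged so that a carrier goes to control and a non-carrier to Exparel (10 of 100 patients).

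Each exchange moves the difference by 2d/50 = 0.2 or 0.4 mg, so five give 1 or 2 mg. Average carrier counts become 20 of 50 against 30 of 50 (40% v 60%). A 5% baseline test of an exactly recorded factor would flag this in about 54% of trials.

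Simulated type I error, with the p < 0.1 screen followed by linear adjustment (200,000 runs per setting):

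| Recording of the factor | d = 5 mg | d = 10 mg |
|---|---|---|
| Unadjusted t-test | 7.9% | 17.1% |
| Recorded exactly | 5.1% | 5.0% |
| Misrecorded in 25% of patients | 7.0% | 12.5% |
| Not recorded | 7.9% | 17.0% |

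With no exchanges, the error is 4.9% to 5.1% throughout. No figure is offered for reading (b).

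**The case against.** The strongest reply is that the only sentence on method and timing puts the random draw after consent. The support for an advance list is a printed form question, not the investigators' answer. The access sentence follows directly on the blinding sentence and does not say that access comes before enrolment; it may only record who knows allocations in a single-blind trial. On that view nothing can be foreseen.

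This stands in part. Foreknowledge follows only if there is a list and access precedes assignment, and the protocol settles neither. But the text as written grants access without limit of time. If the draw is made per patient, the missing log and the possibility of a redraw remain. The protocol needs correcting either way.

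A second reply is that the protocol collects medical, surgical and psychiatric history, medications, substance use, procedure type and laterality, which are plausible cues to opioid need, and will adjust for them. That too stands in part: exact recording restores the 5% level in the illustration. Unrecorded judgement is not covered. A record of which block each patient received is not a log of releases.

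Third, the shifts, the factor's worth, five exchanges all in one direction and the misrecording rate are invented, and nothing shows that staff can reorder patients. This is correct, and the conclusion does not depend on them.

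Lastly, handling of patients removed after assignment and block sizes go beyond concealment proper. That is fair; they are secondary to concealed, logged release.

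**Conclusion.** The concern holds and should be treated as a required correction. The protocol has the unblinded clinic team generate the scheme, grants the surgeons, principal investigator and coordinators access to it, and describes neither concealment nor a logged release. That is a stated rule which permits biased allocation, not merely a missing detail. Under either reading of the scheme a safeguard is absent.

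Bias is possible and has not been shown. Its size cannot be derived from the documents, and the type I error figures depend wholly on assumed shifts. The severity rests on the access rule, the missing concealment and logging, and the fact that concealment cannot be recovered later.

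**What to change.** State whether the scheme is an advance list or a draw per patient. Have the UVA statistician, who has already been consulted (Statistical Considerations, question 6), or IDS generate and hold it; both are options on the form. Replace the access sentence with wording such as:

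> The scheme is held by the statistician or IDS and is not open to any surgeon, investigator or coordinator. Assignments are released one at a time, once eligibility and consent have both been logged, through a locked electronic module, IDS, or sequentially numbered opaque sealed envelopes. Each release is logged and cannot be redrawn. Any block sizes will vary and be withheld from the study team. Every randomized patient is accounted for and analysed in the assigned group.

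The surgeon still learns each individual assignment once it is released, so the single-blind design is unchanged.

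The cost is protocol wording and a small effort to prepare the scheme, release assignments and keep the log. There are no extra patients, visits or procedures. The documents do not give IDS cost or availability; envelopes prepared by the statistician are the alternative.

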2. What are the statistical considerations for the protocol?

Answer/Response:

- This is a randomized, prospective trial that examines the effectiveness of Exparel TAP block (mix of Exparel + plain bupivacaine) compared to plain bupivacaine TAP block at University of Virginia Medical Center between February 2021 and January 2024. Patient information will be kept confidential and all identifying information will be removed. Data collected will involve:
 - General Demographic Data: age, gender, race, ethnicity, medical and surgical history, psychiatric history, medications, drug, smoking, alcohol abuse, occupation
 - Type of Reconstructive Procedure: procedure type, laterality

- TAP block information: liposomal bupivacaine vs. plain bupivacaine
- Post-operative Narcotic Requirement: total mg of oral opioid use in postop period during hospitalization and immediate post-operative period (30 days after discharge).
- Post-operative Data: LOS, pain scores, PONV incidence
- Complications

3. Provide a justification for the sample size used in this protocol.

Answer/Response: The primary outcome variable used for sample size calculation is post-operative narcotic requirement. Since we are unsure of the exact standard deviation for the population in terms of narcotic requirement, but we do have a limited number of patients that will be available for the study, we used four different standard deviations to confirm that we would have enough patients for 80% power ($\alpha = 0.05$) to detect a difference in groups. We believe that the estimate of the standard deviation is most likely in the 10 mg range, so having 50 patients in each group would allow us to detect a difference of 5.66 mg between groups at 80% power.

Sample sizes	Standard deviation	Alpha	Power	Difference that can be detected
50 50	1	0.05	80%	0.57 mg
50 50	5	0.05	80%	2.83 mg
50 50	10	0.05	80%	5.66 mg
50 50	15	0.05	80%	8.49 mg

4. What is your plan for primary variable analysis?

Answer/Response:

Univariate analysis with $\alpha < 0.05$ considered significant, variables with $p < 0.1$ will be included in multivariate analysis to control for potential confounding variables and attempt to determine independent factors associated with outcomes.

Primary outcomes will include post-op recovery data- pain scores and postop narcotic requirement (total mg of opioids) both during hospitalization and up to 30 days after discharge. Secondary outcomes will include LOS and incidence of PONV.

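### Recording the operating surgeon and prespecifying it as a covariate is a cheap gain in precision; leaving it out is not an error

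*Combined protocol and SAP*

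**What the plan says.** Statistical Considerations, item 2, lists the data to be collected: demographics and history, the procedure, the block, opioid use, length of stay, pain scores, PONV and complications. The procedure entry reads "Type of Reconstructive Procedure: procedure type, laterality" and the block entry reads "TAP block information: liposomal bupivacaine vs. plain bupivacaine". Neither names who operated or who placed the block.

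Item 1 allocates patients by random number generator after consent and before surgery, and names no stratification factor. It also says "Surgeons/PI/ study coordinators will not be blinded to randomization", the plural being the only sign that more than one surgeon takes part.

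Item 4 screens variables one at a time and carries those with p < 0.1 into a multivariate model. No covariate is fixed in advance. Item 5 compares length of stay and PONV with two-group tests and calls its multivariate analysis exploratory.

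Item 3 sizes the trial on post-operative narcotic requirement. It states that "the estimate of the standard deviation is most likely in the 10 mg range" and that 50 per arm would "allow us to detect a difference of 5.66 mg between groups at 80% power".

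**The concern.** Two of the three primary outcomes are opioid amounts, in hospital and over the 30 days after discharge. The exclusion criteria describe the usual regimen as including oxycodone as needed, and the documents set no common rule for discharge prescribing or discharge timing. Surgeon habits therefore have room to affect opioid use and length of stay.

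If they do, differences between surgeons stay in the error term of an unadjusted comparison. A variable that is not collected has no planned route through the p < 0.1 screen. If surgeon were collected, that screen would still leave its inclusion to the data. Item 3 says that the number of available patients is limited, so adjusting for a prognostic factor is one of the few ways left to gain precision.

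**Working it through.** **Inputs from the documents (Statistical Considerations, item 3).** 50 per arm ("having 50 patients in each group"), SD 10 mg, alpha 0.05, power 80%, detectable difference 5.66 mg. There is no inflation for dropout, which the Human Participants section expects to be minimal.

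**Inputs assumed.** Three surgeons with equal expected caseloads and evenly spaced means; normally distributed outcomes; total SD held at 10 mg. The share of outcome variance due to surgeon (ρ) is set at 0, 5, 10 and 20%. The documents give none of these except the SD.

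**Step 1: reproduce the plan's figure.** The standard error of the arm difference is 10 × √(2/50) = 2.0 mg. The normal approximation with two-sided alpha gives a detectable difference of 5.60 mg. The noncentral t with 98 degrees of freedom gives 5.659 mg, which matches the stated 5.66 mg. The t method also reproduces the other rows: 0.566, 2.829 and 8.488 mg for SDs of 1, 5 and 15 mg. One-sided alpha gives 4.97 mg and does not match. The sample-size figure is correct as stated.

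**Step 2: detectable difference after adjustment.** Residual SD = 10 × √(1 − ρ). For ρ = 10% this is 10 × √0.90 = 9.49 mg. The detectable difference then follows from the t method, with two further degrees of freedom spent on three surgeons. Using two or five surgeons changes almost nothing.

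**Step 3: power for 5.66 mg.** 8,000 trials of 100 patients were simulated at each ρ and analysed with and without surgeon indicators.

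| ρ | Residual SD (mg) | Detectable difference (mg) | Simulated power, unadjusted | Simulated power, adjusted |
|---|---|---|---|---|
| 0% | 10.00 | 5.66 | 80.0% | 79.3% |
| 5% | 9.75 | 5.52 | 79.5% | 80.7% |
| 10% | 9.49 | 5.37 | 79.7% | 83.1% |
| 20% | 8.94 | 5.06 | 79.4% | 87.0% |

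Simulated type I error was 4.5% to 5.3% across both analyses. The closed formula gives adjusted power of 82.0%, 84.0% and 87.9% at 5, 10 and 20%. That is about one point higher, because it ignores chance imbalance of surgeons between arms; the detectable differences in the table are slightly optimistic for the same reason. In patient numbers, by the normal approximation, 47, 45 and 40 per arm with adjustment would do the work of 50 without it.

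**Step 4: is chance imbalance by surgeon a further harm?** Take two surgeons with 60% and 40% of cases and mean use 10 mg apart. The SD of the imbalance in caseload share is √(0.6 × 0.4 × 2/50) = 0.098, which moves the arm difference by 0.98 mg. As a share of the squared standard error this is 0.98² / 2.0² = 24%. Those two surgeons also contribute 0.6 × 0.4 × 10² = 24 of the total variance of 100, again 24%. The imbalance is the between-surgeon variance already counted in the 2.0 mg standard error.

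**The case against.** The strongest case against is that both premises are assumptions. That several surgeons operate rests on a plural in a list of roles, with no count or caseload. That their practice differs is not stated anywhere. A single site, one recruiting clinic and a usual pain regimen point, if anything, towards shared practice. With little variance between surgeons the gain is close to nothing, and at zero it is a small loss. All of this stands, and it is why the range must start at zero.

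Three stronger readings are tempting, and the documents support none of them.

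- *The comparison is biased or confounded by surgeon.* Patients are randomized individually, so surgeon cannot bias the comparison systematically, and the simulated type I error stays near 5% without adjustment. A lopsided draw of surgeons is possible, but Step 4 shows that it already sits in the standard error.
- *The trial has no slack, so the lost precision makes it underpowered.* Item 3 took the available patients as given and worked back to detectable differences for four SDs, from 0.57 to 8.49 mg. It names no minimum important difference, so 5.66 mg is not a threshold that the trial can miss. A shift of 0.1 to 0.6 mg is small beside the plan's own uncertainty about the SD.
- *Surgeon can never enter the analysis.* The item 2 list is not worded as exclusive, outcomes are taken from Epic, and item 5 allows exploratory modelling. What is missing is a prespecified role.

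It is also fair to say that the timing of surgeon assignment is not documented. The remedy must therefore use the surgeon scheduled at randomization. None of these objections removes a gain in precision that costs very little.

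**Conclusion.** This is a cheap improvement and not a mistake in the plan. Surgeon is absent from the data list, the randomization and every named analysis, and nothing elsewhere in the documents makes up for it. The consequence is limited to precision: about one point of power if surgeon explains 5% of the variance, three to four points at 10% and seven to eight at 20%, against a loss of less than one point if it explains nothing. These figures rest on three surgeons, normal outcomes and an SD of 10 mg, and they apply to the narcotic requirement that was used for sizing. The gain for pain scores cannot be gauged from the documents. The stated 5.66 mg is correct, and the unadjusted comparison is valid.

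**What to change.** - **Item 2:** add a coded operating-surgeon field, taken from the operative record. Record the block operator as well.
- **Item 4:** state that the model for each primary outcome includes the surgeon scheduled at randomization as a categorical covariate, regardless of its p-value. Surgeons with very few cases are pooled into one category, by a rule fixed before outcomes are examined.
- **Block operator:** use it as a covariate only if the operator is fixed before randomization; otherwise keep it as descriptive information.

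The cost is one field, one or two sentences of plan text, and one or two degrees of freedom out of 98. If surgeon has no effect, the price is up to about one point of power. If only one surgeon operates, the change has no effect.
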